APPENDIX C - Definition of Censoring used in analysis of discontinuations due to safety

- Discontinuations due to death, investigator decision and HIV-infection are censored on the discontinuation date
- Participants who exit the study at a scheduled exit visit or at the end of the study are also censored, on the termination date.
- Participants who do not reach the scheduled exit visit and do not discontinue study medications are censored at their last attended visit.
- Permanent discontinuation and/or termination due to participant refusal are treated as competing events, on the discontinuation or termination date, and include: participant unwilling or unable to comply study procedures, injection intolerance, other participant request, or refuse further participation.

The Safety events of interest are:

- Permanent discontinuation due to safety concerns including: clinical/laboratory AE, ISR, CMC recommendation and other clinical reason.

The earliest occurrence of any of the above is selected to determine events versus censored observations versus competing events.

Detailed event/censoring/competing event classifications for reasons for treatment discontinuation or termination:

Events of interest, based on reason for treatment discontinuation:

- CLINICAL AE (PROTOCOL MANDATED)
- LABORATORY AE (PROTOCOL MANDATED)
- CMC RECOMMENDATION BASED ON A CLINICAL EVENT
- CMC RECOMMENDATION BASED ON A LABORATORY VALUE
- CMC RECOMMENDATION FOLLOWING DRUG DISPENSING ERROR
- RASH WHICH THE PARTICIPANT STARTED AFTER THE INITIATION OF INJECTION
- OTHER CLINICAL REASON

Competing events, based on reason for termination:

- PARTICIPANT REFUSED FURTHER PARTICIPATION
- PARTICIPANT RELOCATED, NO FOLLOW-UP PLANNED
- OTHER

Competing events, based on reason for treatment discontinuation:

- PARTICIPANT REQUEST - PARTICIPANT IS UNWILLING OR UNABLE TO COMPLY WITH REQUIRED STUDY PROCEDURES
- PARTICIPANT REQUEST FOR INJECTION INTOLERANCE (AE OR ISR NOT PROTOCOL MANDATED)
- PARTICIPANT REQUEST – OTHER REASON
- PARTICIPANT IS CURRENTLY USING OR PLANNING TO USE PREP OR PEP (OTHER THAN STUDY PRODUCT)
- LOW ORAL ADHERENCE - STEP 1
- PARTICIPANT REFUSED LONG ACTING CONTRACEPTION
- PERCEIVED SIDE EFFECTS OF STUDY DRUG
- POSITIVE PREGNANCY TEST RESULT

Censored observations, based on reason for termination:

- DEATH
- INVESTIGATOR DECISION, SPECIFY
- SCHEDULED EXIT VISIT/END OF STUDY

- HIV INFECTION - STEP 1

Censored observations, based on reason for treatment discontinuation:

- ONE OR MORE REACTIVE HIV TEST RESULTS OR ACUTE HIV INFECTION SUSPECTED
- AS PER CMC: ENROLLMENT ERROR DUE TO DISCORDANT RESULTS (censored on date of randomization)
- HEPATITIS B INFECTION (censored on date of positive test result)

Censored observation, based on loss to follow-up (censored on date of last visit):

(Reason for termination is NULL and Reason for discontinuation is NULL) or Reason for treatment discontinuation = "PARTICIPANT RECEIVED WRONG STUDY PRODUCT AT VISIT 12.0"

Multiple conditions:

Note that a participant may have more than one condition flag indicated for these analyses. The analysis date, ADT, is chosen as the earliest date when multiple conditions are indicated by flag. The event/competing risk/censor variable, CNSR, is chosen as the CNSR value associated with the earliest date when multiple conditions are indicated by flag. If multiple conditions have the same date, the CNSR value is indicated by the earlier value in the following list.

- 1) Safety event,
- 2) Competing events conditions 1, 2, and 3,
- 3) Censoring conditions 1,2, 3, or 4.
- 4) LFU.

Numbers of subjects having had the event of interest, and at risk to have had the event will be shown at selected weekly timepoints under the horizontal axis. The number at risk will be computed as the number of subjects with event times greater than or equal to the given timepoint. The **cumulative** number of events will be computed as the number of subjects with event times **less** than or equal to the event time.

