2. GENERAL DESIGN CONSIDERATIONS

2.1 Purpose:

To evaluate the safety and efficacy of the injectable agent, cabotegravir (CAB LA) compared to daily oral tenofovir disoproxil fumarate/emtricitabine (TDF/FTC), for pre-exposure prophylaxis (PrEP) in HIV-uninfected women.

2.2 Design:

Multi-site, double blind, two-arm, randomized (1:1), controlled superiority trial of the safety and efficacy of CAB LA compared to daily oral TDF/FTC for HIV prevention.

2.3 Population:

HIV-uninfected women at risk for acquiring HIV, 18 to 45 years old.

2.4 Study Size:

The original sample size calculation was to enroll 3200 women. In response to a recommendation from the HPTN Study Monitoring Committee in October 2020, this target was increased to 3350 in LOA 3.

2.5 Study Duration:

Approximately 4.6 years total, with individual participants being followed on randomized study product between 1.6 years (for the last enrolling participants) to approximately 3.6 years (for the earliest enrolling participants), and on oral TDF/ FTC for an additional 48 weeks. Accrual will require approximately 2 years.

2.6 Study Sites:

Study sites will be in sub-Saharan Africa (SSA).

2.7 Study Regimen and Follow-up:

Once randomized to one of two arms, participants will move through the following steps (active study products are shown in bold text):

2.7.1. Step 1, Oral Run-in Phase:

Arm A – **Daily oral cabotegravir (CAB)** and oral TDF/FTC placebo for five weeks plus an HIV prevention package including behavioral risk reduction and adherence counseling, provision of condoms.

Arm B – **Daily oral TDF/FTC** and oral CAB placebo for five weeks plus an HIV prevention package including behavioral risk reduction and adherence counseling, provision of condoms.

Individuals who discontinue study participation after receiving oral product in Step 1, but do not receive any study product in Step 2 will be offered the option to be followed annually with HIV testing until study end.

A participant that becomes HIV-infected during Step 1 of the study will permanently discontinue study product, be terminated from the study, and referred for HIV-related care.

2.7.2 Step 2, Injection Phase:

Arm A – **CAB LA** as a single intramuscular [IM] injection at two time-points four weeks apart and every eight weeks thereafter and daily oral TDF/FTC placebo plus an HIV prevention package including behavioral risk reduction and adherence counseling, provision of condoms.

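### The safety-discontinuation analysis censors death and HIV-related product stops but treats refusal, relocation and pregnancy as competing events, and it counts a fatal adverse event only if a safety stop is recorded by the date of death

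*SAP*

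**What the plan says.** Appendix C of the SAP sorts every exit from blinded product into safety event, competing event or censored observation.

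- **Censored:** "Discontinuations due to death, investigator decision and HIV-infection are censored on the discontinuation date". The detailed lists place DEATH, HIV INFECTION - STEP 1 and INVESTIGATOR DECISION, SPECIFY among the reasons for termination that are censored. A reactive HIV test or suspected acute infection is a censored reason for treatment discontinuation.
- **Competing:** "Permanent discontinuation and/or termination due to participant refusal are treated as competing events, on the discontinuation or termination date". The detailed lists add, among others, relocation and a positive pregnancy test.
- **Safety event:** "Permanent discontinuation due to safety concerns including: clinical/laboratory AE, ISR, CMC recommendation and other clinical reason". The list of these codes is headed "Events of interest, based on reason for treatment discontinuation", so it draws on a different field from the one that holds death.
- **Precedence:** "The earliest occurrence of any of the above is selected to determine events versus censored observations versus competing events". For ties, "If multiple conditions have the same date, the CNSR value is indicated by the earlier value in the following list"; the order is safety event, competing event, censoring, loss to follow-up.

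Section 9.2 plans cumulative incidence displays for treatment discontinuation. On HIV infection, Section 2.7.1 says: "A participant that becomes HIV-infected during Step 1 of the study will permanently discontinue study product". Section 2.7.2 has the same rule for Step 2.

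**The concern.** In a competing-risk analysis, an exit that makes the event of interest impossible is a competing event. Censoring is for women who could still have the event but are no longer observed. Death is the clearest case of the first kind, and an HIV-related permanent stop is another. Appendix C censors both and gives no reason. It treats a positive pregnancy test as competing, although Section 2.7.4 allows a woman to resume product after pregnancy and breastfeeding.

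Two things are at stake. First, the cumulative incidence of safety stops is read as a risk among women in the trial, but part of it is projected onto women who have died or permanently stopped product because of HIV. Second, the coding can lose exits that matter for safety. A woman who dies suddenly from an adverse event may have no product-stop record and would leave as a non-event. A termination by investigator decision is censored even when the specified reason is a safety one. Section 10.2 says that Version 4.0 holds details requested for Clinical Study Report programming, so the rules are likely to be programmed literally.

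**Working it through.** Appendix C gives no rate or sample size to reproduce. The check has two parts.

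**1. How a fatal adverse event is coded** (assuming no earlier competing record)

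| Record | Code under Appendix C |
|---|---|
| Safety-coded discontinuation before death | Safety event (earliest date) |
| Safety-coded discontinuation on the date of death | Safety event (tie rule) |
| Death only, as reason for termination | Censored |

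The same logic applies to an investigator-decision termination: it is censored unless the discontinuation field holds a safety code on or before that date.

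**2. Size of the upward shift from censoring**

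Inputs from the SAP:
- HIV incidence of 2.07 (TDF/FTC) and 1.12 (CAB LA) per 100 person-years (Section 7.2.1). Both follow from the footnote to Table 4.1: 3.5 × (0.15 × 0.48 + 0.52) = 2.07 and 3.5 × (0.15 × 0.80 + 0.20) = 1.12.
- Time T = 3.56 years, the final analysis in Table 2.

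Assumptions not in the SAP:
- Safety-stop hazard s of 0.5% to 3% per year, equal in both arms.
- Death hazard of 0.1% to 0.5% per year.
- Refusal hazard of 5% per year, borrowed from the loss-to-follow-up ceiling in Section 4.1, which is not itself a refusal rate.
- Constant, independent hazards and a standard cumulative incidence estimator.

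Formula, with c the sum of the hazards treated as competing: CIF = s/(s + c) × [1 − exp(−(s + c) × T)].

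Worked case, s = 0.01, death 0.003:
- As coded (c = 0.05): 0.01/0.06 × [1 − exp(−0.2136)] = 3.205%, both arms.
- Death competing (c = 0.053): 0.01/0.063 × [1 − exp(−0.2243)] = 3.189%, both arms. Ratio 3.205/3.189 = 1.005.
- Death and HIV competing, CAB LA (c = 0.0642): 0.01/0.0742 × [1 − exp(−0.2642)] = 3.129%. Ratio 1.025 before rounding.
- Death and HIV competing, TDF/FTC (c = 0.0737): 0.01/0.0837 × [1 − exp(−0.2980)] = 3.079%. Ratio 1.041.

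Over the whole grid of assumptions, the coded figure is too high by 0.2% to 0.9% (relative) for death alone. With HIV added, it is too high by 2.1% to 2.8% in CAB LA and 3.7% to 4.5% in TDF/FTC. In absolute terms the worked case shifts by 0.076 (3.205 − 3.129) and 0.126 (3.205 − 3.079) percentage points.

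The refusal assumption matters little. With neither refusal nor death in the model and s = 0.01, the figures are 3.50% as coded against 3.43% (CAB LA) and 3.37% (TDF/FTC) with HIV competing, again about 2% and 4% too high.

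**The case against.** The strongest reply is that the endpoint is stopping product for safety, not mortality, and that fatal events are reported elsewhere. Section 9.2 requires by-subject listings of deaths, serious adverse events and adverse events leading to discontinuation. The primary safety comparison in Section 7.3.2 counts all adverse events of grade 2 or higher. Appendix C states no hypothesis test. All of this stands and limits the reach of the point.

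It can also be said that investigator decision is a termination reason, while safety stops have their own field with a catch-all for other clinical reasons. That covers every case in which the site fills in the discontinuation field in time. It does not cover a safety reason written only under the termination code.

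Three stronger readings are tempting, and the SAP supports none of them.
- **That a fatal adverse event can never count as a safety exit.** The earliest-date rule and the tie order make it an event when a safety-coded stop is recorded before or on the day of death, with no earlier competing record.
- **That censoring HIV infection creates an artificial difference between arms.** With equal safety hazards, the coded curves agree (3.205% in both). The gap (3.129% against 3.079%) appears only after recoding, and it reflects the real difference in HIV rates.
- **That a large share of safety exits is hidden.** The SAP gives no expected number of deaths, safety stops or deaths due to adverse events. Any such percentage would rest on invented counts, and on the further assumption that no fatal event has a prior stop record.

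**Conclusion.** The point holds as an inconsistency in Appendix C with a small numerical effect. Death and HIV-related stops belong with the competing events under the framework that the appendix itself adopts. Censoring them overstates the cumulative incidence of safety discontinuation by under 1% (relative) for death and by roughly 2% to 4.5% with HIV included, more in TDF/FTC than in CAB LA. Those sizes rest on assumed safety, death and refusal hazards; only the HIV rates and the time horizon come from the SAP.

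The second part, the loss of some fatal adverse events and of safety-based investigator decisions, cannot be sized from the SAP. It works in the opposite direction, by removing events from the numerator, and depends on how often the discontinuation field is left without a safety code. Neither part touches the primary safety comparison, the death listing or the efficacy analyses.

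**What to change.** In Appendix C:
1. Move DEATH, HIV INFECTION - STEP 1 and the discontinuation reason for a reactive HIV test or suspected acute infection from censored to competing events, and align the opening bullets and the tie list.
2. Classify investigator-decision terminations by their specified reason, blinded to arm: a safety reason is an event, any other reason is competing.
3. Keep censoring for scheduled exit, end of study and loss to follow-up.
4. Add a sensitivity analysis that counts a death attributed to an adverse event as a safety event at the date of death, and state the attribution criterion before unblinding. This suits a sensitivity analysis better than the main one, because it widens the endpoint beyond stopping product.

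The cost is one appendix edit, a few recoded status values and a blinded review of what should be a small number of records. The SAP does not show which CRF fields hold the cause of death or the specified reason, so their availability should be confirmed first. If the sponsor prefers to keep the censoring, Appendix C should give the reason and say how deaths due to adverse events are classed.

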Arm B – **Daily oral TDF/FTC** and IM placebo (matching vehicle, identical volume as active injectable product in Arm A) at two time-points four weeks apart and every eight weeks thereafter plus an HIV prevention package including behavioral risk reduction and adherence counseling, provision of condoms.

Step 2 will continue until the required number of endpoints (114) is reached, estimated to be 81 weeks after enrolling the last participant.

Participants who prematurely discontinue blinded study products during Step 2 (having received at least one injection) for any reason other than HIV infection will be offered to transition to 48 weeks of open-label TDF/FTC followed by annual testing through the duration of step 3.

A participant who becomes HIV-infected during Step 2 of the study will permanently discontinue study product, be placed on immediate suppressive ART, and will be facilitated into locally provided ART, and followed at quarterly intervals for 48 weeks after

their last injection prior to diagnosis of HIV in order to test for safety parameters, as well as CD4 cell count and HIV viral load. After 52 weeks, they will be terminated from the study and transitioned to continued HIV-related care.

2.7.3 Step 3, Follow-up Phase:

Arms A and B – Open-label daily TDF/FTC (in order to cover the pharmacokinetic [PK] tail for Arm A participants) will be provided no later than eight weeks after the last injection visit, for up to 48 weeks plus an HIV prevention package including behavioral risk reduction and adherence counseling, and provision of condoms. Participants will then transition to locally available HIV prevention services, including services for PrEP, if available.

Participants with confirmed HIV infection during Step 3 will have their TDF/FTC stopped and be followed quarterly at least for the duration of Step 3, with possible additional assessments and follow-up to be determined by guidance from members of the HIV alias. Study product will be discontinued and participants will be referred for care.

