3. STUDY OBJECTIVES

3.1. Primary Objective:

- **Efficacy:** To evaluate the relative efficacy of oral CAB/CAB LA (oral run-in and injections, Steps 1 and 2) vs. daily oral TDF/FTC for HIV prevention (Steps 1 and 2).
- **Safety:** To evaluate the relative safety of oral CAB/CAB LA (oral run-in and injections, Steps 1 and 2) vs. daily oral TDF/FTC for HIV prevention (Steps 1 and 2).

3.2. Secondary Objectives:

- To compare HIV incidence among participants receiving oral CAB/CAB LA vs. daily oral TDF/FTC (Steps 1, 2 and 3).
- To evaluate relative efficacy of oral CAB/CAB LA vs. oral TDF/FTC in subgroups defined by the baseline factors of age, herpes simplex virus-2 (HSV-2) serostatus, contraceptive method, and body mass index (BMI).
- To describe and model the relationship between HIV incidence and drug concentration, within each arm.
- To describe the distribution and correlates of drug concentration, within each arm.
- To compare the acceptability of and preferences for CAB LA vs. oral TDF/FTC.

3.3. Tertiary Objectives:

- To estimate sexual risk behaviors, as measured by self-report and rates of incident sexually transmitted infections (STIs).
- To compare Grade >2 adverse event (AE) rates in women with baseline BMI $</\geq 30 \text{ kg/m}^2$, within each study arm.
- To compare differences in weight gain and BMI, by arm.
- To compare pregnancy incidence and outcomes between arms.
- To evaluate rates of HIV drug resistance among participants who acquire HIV infection during the study among participants receiving oral CAB/CAB LA vs. oral TDF/FTC.
- To determine plasma concentrations of medroxyprogesterone (DMPA) or norethisterone (NET-EN) or etonogestrel when co-administered with CAB LA.

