4. STATISTICAL CONSIDERATIONS

4.1 Sample Size and Power

The primary analysis will be based on HIV incidence during Steps 1 and 2. As described previously, we assume that participants will be followed between 81 (latest enrollees) and 185 (earliest enrollees) weeks in Steps 1 and 2 (1.6 – 3.6 years), with a uniform distribution of enrollments over a two-year period. Thus, average time in Steps 1 and 2 will be 133 weeks (2.6 years). Sample size calculations are based on the following assumptions:

- Background HIV incidence, in the absence of any PrEP, is 3.5% per year
- Both CAB LA and TDF/FTC are 85% effective when used with 100% adherence
- 2.5% one-sided type I error rate and 90% power at the indicated alternative
- Average follow-up duration of 2.6 years (range: 1.6 – 3.6 years)
- Maximum 5% lost-to-follow-up per year

Table 4.1 presents five scenarios and associated total sample sizes. All are superiority designs. The first scenario assumes that adherence to TDF/FTC and CAB/CAB LA will be 50% and 85%, respectively, averaged over the entire Step 1 and 2 follow-up period. The second and third scenarios assume a higher adherence to TDF/FTC (second line) and lower adherence to CAB LA (80%) (third line) (these scenarios are considered unlikely). The last two scenarios retain the conservative assumption of 80% adherence to CAB LA and assume lower adherence to TDF/FTC of 45% and 48%. The largest blinded trials of TDF/FTC among women in a similar setting have shown even lower adherence than assumed in Table 4.1.

Given this history we believe that a sample size of at least 3,128 (111 events for a fixed sample size trial; we will target 114 events to allow for interim monitoring) provides an adequate degree of robustness against uncertainties in adherence rates to the two drug regimens. The trial will continue until we reach 114 events, or a stopping boundary is crossed (see below).

Table 4.1. Five Case Scenarios

Adherence		HIV Incidence (%/year) ¹				
TDF/FTC	CAB LA	TDF/FTC	CAB LA	RR	Number Events	Sample Size
.50	.85	2.01	0.97	.48	78	2352
.55	.85	1.86	0.97	.52	98	3112
.50	.80	2.01	1.12	.56	125	3590
.48	.80	2.07	1.12	.54	111	3128
.45	.80	2.16	1.12	.52	98	2686

¹Background incidence is reduced by a weighted average of fully adherent and non-adherent individuals e.g. 2.01 = $3.5 * ((1 - .85) * .5 + 1 * (1 - .5))$

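### Appendix C has no censoring at the end of Step 2, so the safety-discontinuation curve can count up to 48 weeks of open-label TDF/FTC as time at risk (minor)

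*SAP*

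**What the plan says.** SAP Appendix C defines events, competing events and censoring for time to treatment discontinuation due to safety (named so in Section 10.2.2).

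- Completers: "Participants who exit the study at a scheduled exit visit or at the end of the study are also censored, on the termination date".
- Women still in follow-up: "Participants who do not reach the scheduled exit visit and do not discontinue study medications are censored at their last attended visit".
- Event: "Permanent discontinuation due to safety concerns including: clinical/laboratory AE, ISR, CMC recommendation and other clinical reason". The product being discontinued is not named.
- Several conditions: "The earliest occurrence of any of the above is selected to determine events versus censored observations versus competing events".

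Neither completion of Step 2 nor entry to Step 3 appears in the detailed lists of events, competing events and censoring reasons. A woman counts as at risk at a timepoint if her event or censoring time is at or beyond it.

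On design, Section 2.7.3 says that open-label TDF/FTC in Step 3, for both arms, "will be provided no later than eight weeks after the last injection visit, for up to 48 weeks". Section 2.5 likewise has participants followed on randomized product "and on oral TDF/ FTC for an additional 48 weeks". The primary safety objective in Section 3.1 is limited to the randomized period: "To evaluate the relative safety of oral CAB/CAB LA (oral run-in and injections, Steps 1 and 2").

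**The concern.** A woman who completes Step 2 has not discontinued for any reason that Appendix C lists, so nothing in the appendix ends her time at risk when randomized product ends. Read literally, she leaves the risk set only at termination, after Step 3. During Step 3 she can no longer discontinue randomized product.

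What follows depends on a point Appendix C leaves open:

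- **Step 3 safety stops are not counted.** The late risk set contains women who cannot have the event, and the cumulative incidence curve flattens.
- **Step 3 safety stops are counted.** Stops of the same open-label drug in both arms are attributed to the randomized arms.

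These are alternatives and do not add up. Neither matches an objective confined to Steps 1 and 2.

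Other analyses in the SAP do set a boundary. Primary efficacy is censored at the end of Step 2 (Section 7.3.1, with transition-date rules in Appendix B). Step 1 adverse events stop at first injection at the latest (Section 7.3.3). The safety OBSP analysis stops 6 or 10 weeks after the last injection (Section 7.3.2). Where Step 3 is wanted, as in secondary analysis (a) of Section 7.3.6, the SAP says so.

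**Working it through.** **Inputs from the SAP.** Section 4.1: "participants will be followed between 81 (latest enrollees) and 185 (earliest enrollees) weeks in Steps 1 and 2", with enrollment uniform over two years. Step 3: up to 48 weeks (Section 2.7.3). Display: cumulative incidence with an at-risk table (Section 9.2).

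**Assumed, because the SAP gives no figure.** A constant safety-discontinuation hazard of 1% per year on randomized product, a full 48-week Step 3, no counted Step 3 events and no data cut before Step 3 ends.

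**The plan's own figure.** Mean time in Steps 1 and 2 is (81 + 185)/2 = 133 weeks, as stated in Section 4.1.1, Table 1.

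**Crude person-time.** A completer contributes 133 + 48 = 181 weeks on average, of which 48/181 = 26.5% is off randomized product. This describes a crude rate, whereas the planned display is a curve.

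**Curve.** At week t:

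- share of women on randomized product: 1 to week 81, then (185 − t)/104
- share counted at risk under Appendix C: the smaller of 1 and (233 − t)/104, since 185 + 48 = 233

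The estimated hazard is the true hazard times the ratio f(t) of these shares: 1 to week 81, (185 − t)/104 for weeks 81 to 129, and (185 − t)/(233 − t) for weeks 129 to 185.

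Integrating f over 0 to 185:

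- weeks 0–81: 81
- weeks 81–129: (104² − 56²)/(2 × 104) = 36.9
- weeks 129–185: 56 − 48 × ln(104/48) = 18.9
- total 136.8 weeks, and 136.8/185 = 0.740, so the cumulative hazard is 26% low at the very end

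Cumulative incidence at 1% per year:

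| Week | On product | Counted at risk | Censored at end of Step 2 | Appendix C | Shortfall |
|---|---|---|---|---|---|
| 81 | 100% | 100% | 1.55% | 1.55% | 0% |
| 105 | 77% | 100% | 2.00% | 1.95% | 2.6% |
| 129 | 54% | 100% | 2.45% | 2.24% | 8.5% |
| 133 | 50% | 96% | 2.53% | 2.28% | 9.6% |
| 153 | 31% | 77% | 2.90% | 2.46% | 15% |
| 177 | 8% | 54% | 3.35% | 2.59% | 23% |
| 185 | 0% | 46% | 3.49% | 2.60% | 26% |

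The incidences in the last row are taken just before week 185, because nobody is on product at week 185 itself.

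**Sensitivity of the shortfall at week 185.**

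- Constant hazard of 0.5% to 5% per year: 26% to 24%.
- Competing hazard of 5% per year added: 24%.
- Hazard four times higher in the first 26 weeks: 18%.
- Hazard six times higher in the first 52 weeks: 11%.
- Step 3 lasting 24 or 12 weeks: 20% or 14%.
- Step 3 stops counted at an assumed 0.5% per year: effective exposure 136.8 + 0.5 × (185 − 136.8) = 160.9 weeks, so 1 − exp(−0.01 × 160.9/52) = 3.05% against 3.50% at week 185, about 13% low. At 1% per year there is no shortfall, but the curve then mixes two products.

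**The case against.** The strongest reply is that little Step 3 time may enter. Section 10.2 ties this version of the SAP to programming for the Clinical Study Report. If that report is cut when the blinded portion ends, women still in follow-up have no termination date and fall under the last-attended-visit rule. The scheduled exit visit is not defined as the last Step 3 visit, and Section 4.1.1, Table 1 uses EOS for the end of Steps 1 and 2. The safety objective could also be taken to restrict Appendix C to Step 1 and 2 data.

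This limits the size but does not repair the rule. Appendix C states no data cut, its last-attended-visit fallback is not confined to Steps 1 and 2, the EOS note belongs to a sample-size table, and the study-closure censoring in Appendix B is written for efficacy.

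It is also fair that the consequence is small. The primary safety comparison is the rate of grade 2 or higher adverse events (Section 7.3.2), and its OBSP version already ends follow-up soon after the last injection. Section 9.2 describes the safety reporting as descriptive.

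A reader might infer that the treatment contrast is pulled toward no difference by a calculable amount. The documents do not support that: the SAP specifies no hazard ratio, rate ratio or test for safety discontinuation, and if Step 3 stops are not counted, both arms are diluted alike.

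**Conclusion.** The rule is wrong as written, but the matter is minor and touches one descriptive safety display. If the data include Step 3, Appendix C keeps completers at risk for up to 48 weeks after randomized product has ended.

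A reader might infer from the 48/181 share that the whole curve is about a quarter too low. It is not. The curve is unchanged to week 81 and about 10% low at the average follow-up. The 26% is an upper bound, reached only at week 185, where the properly censored risk set is empty. It rests on uniform 81 to 185 week follow-up, a constant hazard, a full 48-week Step 3, no counted Step 3 events and no earlier data cut. Early-weighted hazards bring it to about 11–18%, and a 12- to 24-week Step 3 to about 14–20%. A cut at the end of the blinded portion would remove most of it.

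**What to change.** Add to Appendix C: women still on randomized product are censored at the earlier of Step 3 Day 0 (visit 33.0) and the study-wide transition date; only discontinuations of randomized product in Steps 1 and 2 count as events or competing events. Keep termination-date censoring for exits before that point.

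The cost is one SAP sentence and one derived date, with no new data. Late displayed percentages would be slightly higher.

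### Appendix C handles error-driven product stops inconsistently: one is coded as loss to follow-up although a discontinuation reason is recorded, another counts as a safety event with no adverse event required

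*SAP*

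**What the plan says.** Appendix C first gives general rules and then assigns each recorded reason to a class.

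- **Safety events, general definition:** "Permanent discontinuation due to safety concerns including: clinical/laboratory AE, ISR, CMC recommendation and other clinical reason".
- **Safety events, detailed list:** the reasons include "CMC RECOMMENDATION FOLLOWING DRUG DISPENSING ERROR".
- **Censoring at last visit, general rule:** "Participants who do not reach the scheduled exit visit and do not discontinue study medications are censored at their last attended visit".
- **Last-visit censoring, detailed list:** under the heading "Censored observation, based on loss to follow-up (censored on date of last visit") stand two groups. One is women with no recorded reason for either termination or discontinuation. The other is women whose recorded reason for stopping treatment is "PARTICIPANT RECEIVED WRONG STUDY PRODUCT AT VISIT 12.0".
- **Another operational error involving the CMC:** "AS PER CMC: ENROLLMENT ERROR DUE TO DISCORDANT RESULTS (censored on date of randomization") is listed among the censored observations.
- **Ties:** "If multiple conditions have the same date, the CNSR value is indicated by the earlier value in the following list". In that list safety events come first and loss to follow-up comes last.

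The SAP's summary of changes (10.2.2) says these definitions were added in Version 4.0, which 10.2 describes as prepared for Clinical Study Report programming. The lists therefore drive the derivation directly.

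**The concern.** A reader will take the curve of discontinuation due to safety as a tolerability result. Two features of the coding do not fit that reading.

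First, a stop that follows a supply error enters as an event whether or not anything adverse happened to the participant. Second, a stop with a known reason is handled as if the participant had simply disappeared. The date that closes her follow-up is then her last visit, not the date she stopped product. The appendix states no principle that separates the two codes, so a programmer or reader cannot tell why one error-driven stop is an event and the other is loss to follow-up.

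At stake is the accuracy of a descriptive display and its at-risk table, not a formal test.

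**Working it through.** The SAP gives no figure to reproduce here, so the check sets the rules of Appendix C against each other and then scales the effect.

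**Step 1. The wrong-product code against the general censoring rule.** Last-visit censoring has two conditions: the participant does not reach the scheduled exit visit, and she does not stop study medication. The wrong-product code is identified by the field for reason for treatment discontinuation. A woman with this code has a recorded stop and fails the second condition, so the detailed list contradicts the general rule.

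**Step 2. What follows for time at risk.** Appendix A shows that visit 12.0 is Week 33, in Step 2. SAP 2.7.2 offers women who stop blinded product early in Step 2, for reasons other than HIV infection, 48 weeks of open-label TDF/FTC followed by annual testing. Her last visit may therefore fall well after the stop. Appendix C takes the earliest flagged date, but the product stop carries no flag of its own under this code. Unless another flag is earlier, she counts as at risk of a permanent product stop that has already happened. This applies only if she attended visits after stopping.

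**Step 3. The dispensing-error code against its neighbours.**

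| Recorded reason | CMC involved | Clinical or laboratory basis stated | Class |
|---|---|---|---|
| CMC recommendation, clinical event | yes | yes | safety event |
| CMC recommendation, laboratory value | yes | yes | safety event |
| CMC recommendation, dispensing error | yes | no | safety event |
| Enrollment error with discordant results | yes | no safety basis stated | censored at randomization |
| Wrong product at visit 12.0 | not stated | no | loss to follow-up, last visit |

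CMC involvement alone does not make a stop a safety event, since the enrollment error is censored. A clinical or laboratory basis does not explain the split either, since the dispensing-error code has none.

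**Step 4. Scale.**
- SAP 4.4 gives about 3,350 participants and SAP 4.2 gives 1:1 randomization: 3350 / 2 = 1,675 per arm.
- One participant moved between event and non-event: 1 / 1675 = 0.0006, or about 0.06 percentage points of that arm's crude proportion.
- The SAP gives no count of such stops. Assuming one to five in one arm, the range is 0.06 to 5 / 1675 = 0.30 percentage points.

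This scale applies to the dispensing-error code. The wrong-product code does not add an event; it can only add time at risk.

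**The case against.** The strongest reply is that the dispensing-error code follows the SAP's definition. That definition names a CMC recommendation among the safety reasons without qualification, and it speaks of safety concerns, which is wider than drug toxicity. This stands in part: the code does not breach an explicit rule, and a broad event class could have been intended. It does not explain why the enrollment error, which also involves the CMC, is treated differently.

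Several stronger readings are tempting and are not supported.

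- **That Appendix C censors all its other non-safety stops on the discontinuation date.** The rule "Discontinuations due to death, investigator decision and HIV-infection are censored on the discontinuation date" covers only those three reasons. Enrollment error and hepatitis B have their own dates, and participant request, low oral adherence, refused contraception and pregnancy are competing events. The conflict in Step 1 does not need a uniform rule.
- **That the two codes describe the same error.** One records a CMC recommendation and the other does not. What can be said is that both are error-driven and that no distinguishing rule is given.
- **That the wrong-product participant certainly adds time at risk after stopping.** This depends on her later attendance, which the SAP does not show.
- **That the safety curve is materially inflated.** Five stops in one arm, against an assumed true proportion of 1 to 2%, would be a relative inflation of 0.30 / 2 = 15% to 0.30 / 1 = 30%. Neither the five nor the 1 to 2% appears in the SAP.

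The tie rule adds no separate fault, because it ranks every safety event first. The visit-specific wording also suggests a code for one or very few women.

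**Conclusion.** The inconsistency is real but small. The firmer half is the wrong-product code: it is a recorded treatment stop placed under a last-visit rule that the same appendix keeps for women who did not stop. The softer half is the dispensing-error code. It sits within the literal wording of the event definition, but has no stated adverse-event basis and is treated differently from another operational error involving the CMC.

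The effect is about 0.06 percentage points per reclassified participant, assuming equal arms of 1,675. The total is unknown because no counts are given, and it is probably slight. SAP 7.3 sets no formal test for this endpoint, and 9.2 mentions treatment discontinuation only as a cumulative-incidence display. The primary efficacy analysis (7.3.1) and the primary comparison of grade 2 or higher adverse events (7.3.2) do not use these codes. Low priority.

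**What to change.** Amend Appendix C and the matching CNSR and ADT derivations as follows.

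1. Take the visit 12.0 wrong-product reason out of the loss-to-follow-up rule, leaving there only women with no recorded reason, and end her follow-up on the date of product discontinuation.
2. Give this code and the dispensing-error code one shared non-safety class, dated at product discontinuation. Either censoring or a competing event would match some of the appendix's other non-safety stops. The competing-event option deserves thought, because a permanent stop rules out a later safety stop. State the choice and the reason.
3. Count a dispensing-error stop as a safety event only when a clinical or laboratory adverse event is recorded as the reason for stopping.
4. Report the number of stops under each code by arm beside the display.

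The cost is two code reassignments and one sentence of rationale. The only extra work is to check the adverse-event record for each dispensing-error stop, so that a true safety stop is not lost. The SAP's Introduction already requires changes, and their timing relative to unblinding, to be documented, and this one should be entered there. It concerns analysis coding only and implies nothing about how dispensing errors should be managed clinically.
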